4.3 Sample size

The sample size for the phase 2 trial is based on non-inferiority of the BE-PEP regimen compared to the SDR-PEP regimen in terms of adverse events, in particular QTc prolongation. We assume that in the SDR group the mean QTc will be equal to that of a reference population, i.e. 384 ms (SD 20 ms) based on the Fridericia correction method. [29]

The sample size calculations were performed by simulation, in a scenario where there is truly no difference between the standard and experimental treatment. A sample size of 64 patients are required per arm to achieve 80% power in the comparison that the upper limit of a one-sided 95% confidence interval will be below the non-inferiority limit of +10 ms.

For this part of the trial we have selected a village with a total recorded population of 908, 51% of whom are aged 18 years or above. As explained in chapter 4.2 above, as a matter of precaution we will first enroll adults and preliminarily assess their outcomes before we will start enrolling minors. The numbers of adults to be enrolled will be proportional to the observed age distribution at the time of the 2022 survey. To arrive at an accurate estimate of mean QTc for adults as well as for minors, we will recruit 150 participants per study arm, approximately 75 adults and 75 minors.

Overall, all ages combined, our intended sample size of 150 in each arm, which will provide 99% power to show that the upper limit of a one-sided 95% confidence interval will be below the non-inferiority limit of +10ms, assuming that in the larger population QTc does not differ between those receiving SDR-PEP and those receiving BE-PEP. Sample size calculations were done in R version 4.0.2.[30]

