Post meeting note: Additional data have been provided during the meeting supporting the potential benefit and rationale for the proposed combination regimen and mainly for the proposed dose (regimen). These have, however, not been assessed in detail.

- The **major safety issues** are cardiovascular and hepatic safety:
 - The risk for QT interval prolongation related to bedaquiline administration is considered not being higher than during MDR-TB treatment with bedaquiline. The main driver of the cardiovascular toxicity is its metabolite M2. The observed M2 Cmax in the thorough QT study with a bedaquiline 800 mg single dose was found to be lower than the Cmax at steady state of M2 when compared to tuberculosis dosing of bedaquiline. The risk for QT interval prolongation cannot be excluded and caution is still warranted, see warnings and precautions in the bedaquiline SmPC.

Post-meeting note: In the thorough QT study, the upper bound of the **95% one-sided** confidence interval for the largest time-matched mean effect of the drug on the QTc interval must exclude 10 ms, while the 90% confidence interval is reported in the study report. QT interval prolongation is a known risk for bedaquiline.

Post-meeting note: More detailed modeling and simulation data can be provided to predict the expected QT interval prolongation, though details have not been assessed as this has been provided post meeting.

- Risk for overlapping hepatic toxicity with co-administration of rifampicin and bedaquiline is considered of more limited importance as it is usually reported after multiple doses of bedaquiline. It should however, be discussed by the applicant.

A nested phase 2 study is recommended with stringent evaluation of safety of the proposed rifampicin/bedaquiline combination regimen, including monitoring of ECG and liver enzymes and with more stringent exclusion criteria related to these safety issues.

Post-meeting note: The safety assessment and discussion during the meeting focused mainly on the major safety issues (related to cardiovascular and hepatic safety), though other acute side effects, some reported for both bedaquiline and rifampicin, should be taken into consideration as well, e.g. gastro-intestinal (nausea, vomiting), nervous system-related (headache, dizziness) and cutaneous reactions, as these can have an impact on the safety, tolerability and acceptability of the drug regimen.

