#### **Post PEP measurements**

ALT/AST results after study drug administration (day 14 and 30) will be described both numerically and as proportions above the normal range ( $> 3$  ULN) using 95% Wilson confidence intervals pooled and by study arm. Chi-square or Fisher's exact test will be used to compare the proportions between the two study arms. The difference of the days 14 and 30 ALT/AST result with the results at baseline will be tabulated broken into categories ( $<0$ , 0-9, 10-19, etc).

The individual differences between baseline QTc and ALT/AST results and results from day 1 (QTc) or day 14 (ALT/AST) will be calculated. The difference will be described in 20ms categories ( $<0$ , 0-19, 20-39, 40-59 etc.) for QTc and in 10 U/L categories ( $<0$ , 0-9, 10-19, etc) for ALT and AST. Analysis of covariance (ANCOVA) or an equivalent regression model correcting for the baseline values of ALT/AST will be used similar to the methodology described for the primary objective. Alternatively, the individual difference scores will be calculated by subtracting the ALT/AST values at baseline from the ones at day 14 or 30. The difference scores will be compared using a two-sample t-test.

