### **6.5. Other aspects**

#### ***6.5.1. Subgroup analyses***

Since this is a stratified randomized trial, all analyses will be done by age-group.

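### ALT/AST are compared between arms only in U/L, with an open choice that includes the less precise change-score t-test; a log-scale ANCOVA is worth adding beside the raw one, not in place of it

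*SAP*

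**What the plan says.** SAP 6.2, under Post PEP measurements, lists a regression first: "Analysis of covariance (ANCOVA) or an equivalent regression model correcting for the baseline values of ALT/AST will be used", modelled on the QTc method of SAP 6.1. It then gives an alternative, in which baseline ALT/AST is subtracted from the day-14 or day-30 value: "The difference scores will be compared using a two-sample t-test". Nothing says which of the two will be reported. No transformation, ratio or rank method is named. The same section tabulates changes in 10 U/L categories and compares the proportions above 3 x ULN by chi-square or Fisher's exact test.

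The comparison is secondary. It has no stated margin, alpha, SD or power, and SAP 6.5.2 makes no multiplicity adjustment. SAP 6.5.1 adds that "all analyses will be done by age-group", so it is repeated in groups that Protocol 4.3 puts at "approximately 75 adults and 75 minors" per arm.

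**The concern.** Transaminases are usually taken to be right-skewed, with changes that grow with the level. If that holds here, a few large values can move an arm mean in U/L and inflate its standard error, so that a modest general rise is harder to see. The change-score alternative also gives up precision that baseline adjustment would keep. An open choice between two tests allows selection after the data are seen.

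The stake is moderate. The regulatory opinion in Annex 1 of the protocol says the major safety issues "are cardiovascular and hepatic safety", and Table 3 of the protocol schedules no liver tests in phase 3. Phase 2 is therefore the only planned comparison of these enzymes between arms.

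**Working it through.** **Inputs from the documents.** There are 150 per arm (Protocol 4.3). ULN is 55 U/L for ALT and 48 for AST (SAP 3.2). Baseline above 3 x ULN is excluded, so ALT up to 3 x 55 = 165 U/L can be enrolled.

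**Assumed, because the documents give nothing.** Log-normal values with median 20 U/L; log-SD s = 0.3 to 0.6; baseline to day-14 correlation r = 0.5 to 0.85 on the log scale; a rise of 10 to 20%; two-sided 5%.

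**The plan's own figure.** The only phase 2 power statement at this size is for QTc: "our intended sample size of 150 in each arm, which will provide 99% power", with margin 10 ms and SD 20 ms. SE = 20 x sqrt(2/150) = 2.309; 10/2.309 - 1.645 = 2.685; power = 0.996. It reproduces. No such figure exists for ALT/AST.

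**Why the t-test is weaker.** With equal variances, a change score has variance 2 x SD^2 x (1 - r) and an ANCOVA residual has SD^2 x (1 - r^2). Their ratio, ANCOVA to change score, is (1 + r)/2, which is 0.80 at r = 0.6.

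**Closed-form check (s = 0.5, r = 0.6, 10% rise).**
- Raw mean = 20 x exp(0.125) = 22.66. Raw SD = 22.66 x sqrt(exp(0.25) - 1) = 12.08. Raw correlation = (exp(0.15) - 1)/(exp(0.25) - 1) = 0.570. Mean rise = 2.266 U/L.
- Change t-test: variances 125.5 (SDR-PEP) and 139.5 (BE-PEP); SE = sqrt(265.0/150) = 1.329; 2.266/1.329 - 1.96 = -0.255; power 0.40.
- Raw ANCOVA: SE = sqrt(145.9 x (1 - 0.570^2) x (1 + 1.21)/150) = 1.205; 2.266/1.205 - 1.96 = -0.079; power 0.47.
- Log ANCOVA: SE = 0.5 x sqrt(2 x 0.64/150) = 0.0462; 0.0953/0.0462 - 1.96 = 0.103; power 0.54.

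**Simulated power.** The isolated high values in rows 3 to 5 occur in both arms alike.

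| Setting (150 per arm unless stated) | Change t-test | Raw ANCOVA | Log ANCOVA |
|---|---|---|---|
| s 0.5, r 0.6, +10% | 0.40 | 0.47 | 0.54 |
| s 0.5, r 0.6, +15% | 0.71 | 0.78 | 0.85 |
| s 0.5, r 0.6, +10%, 1% with four-fold values | 0.31 | 0.36 | 0.48 |
| s 0.35, r 0.6, +12%, 1% with four-fold values | 0.64 | 0.67 | 0.89 |
| s 0.5, r 0.7, +15%, 3% with four-fold values | 0.47 | 0.48 | 0.80 |
| s 0.5, r 0.7, +15%, 75 per arm | 0.53 | 0.57 | 0.65 |
| Raw values normal (mean 22, SD 8), r 0.7, +10% | 0.85 | 0.89 | 0.75 |
| Four-fold rise in 5% of BE-PEP only, s 0.35, r 0.6 | 0.61 | 0.63 | 0.38 |

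Across log-normal settings at 150 per arm without isolated spikes, and with raw ANCOVA below 90%, log ANCOVA gained 2 to 12 points over it (median 7). At s = 0.3 the gain was 0 to 2. Type I error was 4.4 to 5.2% for every method.

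The t-test's deficit against raw ANCOVA depends on the correlation. It is about 2 to 7 points at r = 0.6 and 11 at r = 0.5 (0.62 against 0.73, s = 0.5, +15%). It is nil within simulation error at r = 0.85 with 3% spikes.

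**One extreme value.** An ALT rising from 55 to 8 x 55 = 440 U/L moves a mean of 150 by 385/150 = 2.6 U/L. A 10% rise at the assumed median is 2 U/L.

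**The case against.** A reader might infer that the U/L analysis should be replaced by a log analysis, on the ground that large individual rises stay visible in the change categories and the proportions above 3 x ULN. The documents do not support that. The categories are descriptive. A four-fold rise from 20 is 80 U/L, well under 165, so the threshold test misses it: in the last row of the table it detected almost none. Without the raw ANCOVA, no sensitive between-arm test would remain for a rise confined to a few people. This objection stands.

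A reader might also infer that a few large values will dominate this dataset. Nothing in the documents shows that. No SD or skew is given, and baseline values above 3 x ULN, jaundice, reported hepatitis and a history of liver disease are all exclusions.

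Three further points limit the weight of the concern:
- The t-test is only the alternative. Baseline adjustment is listed first, and the text does not expressly forbid a log model.
- The plan's liver signals are individual and on the U/L or ULN scale: above 3 x ULN, a rise of 35 or more, above 8 x ULN. It never names a general 10 to 15% shift as a target. Annex 1 also gives overlapping hepatic toxicity lesser weight, because it is usually seen after repeated bedaquiline doses.
- No decision rule hangs on the comparison. Protocol 9.2.2 plans no formal comparison of ALT/AST elevations between arms, so the SAP already goes further.

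These points lower the importance. They do not justify keeping the t-test or leaving the choice open.

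**Conclusion.** The concern holds in a limited form. SAP 6.2 leaves two U/L analyses open, and the change-score t-test had no material advantage over raw ANCOVA in any setting examined. Its cost is about 2 to 7 points of power at a correlation of 0.6. A log-scale ANCOVA adds sensitivity to a general proportional rise: 0 to 12 points over raw ANCOVA without extreme values, and more with a few. It loses sensitivity if values are near normal or if the rise sits in a few participants. The two scales answer different questions, so the case is for adding the log model, not for substituting it. Every figure depends on an assumed distribution, correlation and size of rise. This is a minor improvement to a secondary analysis and does not affect the QTc primary outcome or the pause criteria.

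**What to change.** In SAP 6.2:
- Delete the change-score t-test for ALT/AST.
- Prespecify, for each enzyme, day-14 ANCOVA in U/L on arm, baseline value and age stratum. Fix day 14 as the time point: under Protocol 5.1, day-30 tests follow only a day-14 elevation event or a rise of 35 or more, so a day-30 comparison would rest on a selected subset.
- Add the same model on log(ALT) and log(AST) with log baseline, reported as a geometric mean ratio with 95% CI.
- Keep the 10 U/L change categories and the proportions above 3 x ULN.

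The cost is a few lines of SAP text and no new data. The downside is one extra secondary result per enzyme, unadjusted for multiplicity, and a ratio to be read beside a U/L difference.

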### **6.3. General safety aspects**

Adverse events (AEs) will be coded using the Medical Dictionary for Regulatory Activities (MEDDRA) and will be reported based on MEDDRA preferred terms and body systems. All AEs will be analyzed based on counts of subjects with a specific category and not on counts of individual adverse events. The relationship between AEs and treatment is determined by the investigator and categorized as "drug-related" if possibly, probably or definitely related to treatment. A general summary of safety events will be presented by treatment arm. Potentially frequent adverse events such as gastro-intestinal (nausea, vomiting), nervous system-related (headache, dizziness) and cutaneous reactions will be tabulated and presented using standard descriptive statistics (counts, percentages and 95% Wilson confidence intervals). AEs related to liver function, such as hepatitis, liver function elevation, transaminitis, liver toxicity, etc, will be grouped into one category. Fisher's exact test will be used to compare the association between the observed frequencies between the two treatment arms. A second table containing each reported AE by preferred terms and body system will be included in the analysis. All safety events will be presented both pooled and by time point (day 0, day 1, day 14 and day 30).

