9.2.2. Secondary analysis

Baseline frequency of ALT/AST elevations and QTc prolongations in the population, before and after study drug administration will be estimated using 95% confidence intervals for each time point and by study arm. No formal comparison will be done between time points or between arms.

Potentially frequent adverse events such as gastro-intestinal (nausea, vomiting), nervous system-related (headache, dizziness) and cutaneous reactions will be tabulated and presented using standard descriptive statistics. A comparison between the two arms will be done using Fisher's exact test.

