## 2. Study design and objectives

### 2.1. Study design

This is a single-site, randomized, non-inferiority, phase 2 clinical trial, comparing the safety between a single dose rifampicin (SDR-PEP) and single dose bedaquiline plus rifampicin (BE-PEP) among contacts of recent leprosy cases. Safety will be closely monitored and evaluated by an independent data and safety monitoring board (DSMB). The study setting is the village of Gégé, Anjouan, that is part of arm 1 of the PEOPLE trial in which 8 new cases have been diagnosed since 2019 but no PEP has been provided.

During the final survey round of the PEOPLE study, all individuals in the village aged 5 years or above, weighing 20 kg or above and not currently suffering from leprosy will be enumerated and screened for the study inclusion and exclusion criteria (see 5Description of analysis populations Description of analysis populations for more details).

Three hundred of the eligible individuals from the village will be stratified proportionally over three age-groups (18 years and above, 13-17 years, and 5-12 years) and will be randomized (1:1) into one of the two study arms:

- Arm 1: single dose of bedaquiline plus rifampicin (BE-PEP) (n=150)
- Arm 2: single dose of rifampicin (SDR-PEP) (n = 150)

Randomization will occur sequentially, first enrolling persons above 18 years of age. Provided no concerning adverse events are observed, the randomization and enrollment will continue for the 13-17 years old age category. Again if no concerning adverse events are observed, the enrollment will proceed for children aged 5-12 years old. The remainder of the population of this village aged 2 years and above will be offered single dose rifampicin as per WHO recommendations.

All randomized participants will be followed up closely with active monitoring for adverse events, including measurement of the corrected QT interval and liver function, before and after administration, as well as any other adverse events, including but not limited to gastro-intestinal (nausea, vomiting), nervous system-related (headache, dizziness) and cutaneous reactions.

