## 2.3. Study hypothesis

It is hypothesized that BE-PEP is not inferior the SDR-PEP in terms of safety.

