## **6. Statistical Methods**

### **6.1. Primary safety analysis**

The main objective about the difference in QTc between the two arms 24 hours after treatment administration will be assessed by calculating the 95% confidence interval for the difference.

Non-inferiority is established if the upper limit of a one-sided 95% confidence interval around the difference in means QTc 24 hours after treatment administration (BE-PEP - SDR-PEP) is below the non-inferiority limit of +10 ms.

Analysis of covariance (ANCOVA) or an equivalent regression model correcting for the baseline values of QTc will also be used to assess the primary objective. Alternatively, the individual difference scores will be calculated by subtracting the QTc values at baseline from the ones at day 1. The difference scores will be compared using a two-sample t-test.

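### Phase 2 hypothesises non-inferior safety overall, but only mean QTc has a margin and an upper bound; adverse-event frequencies and ALT/AST elevations above 3x ULN get tests of no difference, with no interval for the excess risk

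*SAP*

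**What the plan says.** The hypothesis in SAP 2.3 names no endpoint: "It is hypothesized that BE-PEP is not inferior the SDR-PEP in terms of safety". Protocol 4.3 says the phase 2 sample size rests on "non-inferiority of the BE-PEP regimen compared to the SDR-PEP regimen in terms of adverse events, in particular QTc prolongation". The calculation that follows uses mean QTc alone.

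The size is 150 per arm: "we will recruit 150 participants per study arm, approximately 75 adults and 75 minors". SAP 2.1 confirms that participants "will be randomized (1:1) into one of the two study arms".

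The only rule for declaring non-inferiority is in SAP 6.1. It requires that the upper limit of a one-sided 95% interval for the difference in mean QTc at 24 hours "is below the non-inferiority limit of +10 ms".

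Other safety endpoints are handled differently:

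- **Common adverse events (SAP 6.3):** counts, percentages and Wilson intervals, then "Fisher's exact test will be used to compare the association between the observed frequencies between the two treatment arms". Protocol 9.2.2 also names Fisher's test for these events.
- **ALT/AST above 3x ULN (SAP 6.2, post-PEP measurements):** Wilson intervals, pooled and by arm, then "Chi-square or Fisher's exact test will be used to compare the proportions between the two study arms".
- **ALT/AST as continuous values (SAP 6.2):** baseline-adjusted ANCOVA, or a t-test on change scores.

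Protocol 9.2.2 says of ALT/AST elevations and QTc prolongations: "No formal comparison will be done between time points or between arms".

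**The concern.** A non-inferiority hypothesis is supported when an upper confidence limit excludes a stated excess. Fisher's test and the chi-square test take no difference as the null hypothesis, so they can show harm but cannot show its absence. For adverse-event frequencies and binary liver elevations, the plan therefore states a hypothesis that its analysis cannot address. The Wilson intervals describe proportions within an arm or pooled over arms; none is an interval for BE-PEP minus SDR-PEP.

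At stake is what the DSMB sees before it advises on a phase 3 trial sized at 75,152 analysable subjects across two arms. Because its advice is a matter of judgement, it needs to know how large an excess remains compatible with the data. A p-value does not say.

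There is also a plain conflict: the SAP tests ALT/AST elevations between arms, and the protocol says that they will not be formally compared.

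**Working it through.** **Inputs from the documents.** 150 per arm, 1:1; QTc margin 10 ms, SD 20 ms, true difference 0, one-sided 95% limit.

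**Assumptions, because the documents give none.** Control event rates of 1% to 20%; a two-sided 5% level for Fisher and chi-square.

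**1. The plan's own figure.** Power for QTc = Φ(margin / (SD × √(2/n)) − 1.645). The standard error is 20 × √(2/150) = 2.309 ms, and 10 / 2.309 = 4.330. Then Φ(4.330 − 1.645) = Φ(2.685) = 0.996. The stated 99% is reproduced, so the QTc comparison is well powered. No power is stated for any adverse-event or liver comparison.

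**2. Chance that the planned tests miss a doubling.** Power is the sum, over all pairs of counts (x, y), of the two binomial probabilities for those pairs with p ≤ 0.05. The miss rate is one minus that sum. At 150 per arm:

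| SDR-PEP rate → BE-PEP rate | Fisher misses | Chi-square misses |
|---|---|---|
| 1% → 2% | 98% | 91% |
| 2% → 4% | 91% | 84% |
| 5% → 10% | 70% | 63% |
| 10% → 20% | 37% | 31% |
| 15% → 30% | 15% | 12% |
| 20% → 40% | 4% | 3% |

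SAP 6.5.1 calls for all analyses by age group. In the adult stratum, about 75 per arm, Fisher misses 5% → 10% 87% of the time and 10% → 20% 68% of the time. The two child strata share the other 75 or so per arm, so power there is lower still.

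**3. What a non-significant result can leave open.** Take 8/150 under SDR-PEP and 17/150 under BE-PEP. Fisher's p is 0.09. The risk difference is 11.33 − 5.33 = 6.00 points. Newcombe's limit uses the Wilson limits of each arm, here with z = 1.645:

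- Wilson lower limit for 8/150: 3.03%.
- Wilson upper limit for 17/150: 16.29%.
- Upper limit of the difference = 6.00 + √((16.29 − 11.33)² + (5.33 − 3.03)²) = 6.00 + √(24.60 + 5.29) = 11.5 points.

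A liver-type example is 0/150 versus 5/150: Fisher's p is 0.06 and the upper limit is 6.7 points.

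**4. What the proposed interval would deliver.** With equal observed rates p, the one-sided 95% upper limit is about 1.645 × √(2p(1 − p)/150): 2.7 points at 2%, 4.1 at 5%, 5.7 at 10% and 7.6 at 20%.

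**5. Could adverse events carry their own margin at this size?** n per arm = (1.645 + 0.842)² × 2p(1 − p) / margin², for 80% power with equal rates. At p = 5% and a 5-point margin, 6.183 × 0.095 / 0.0025 gives 235. At p = 10%, a 5-point margin needs 446 and a 10-point margin needs 112. These margins are illustrations only. With 150 per arm, a 5-point margin is out of reach at these rates.

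**The case against.** The strongest reply is that the test in question decides nothing. Under protocol 2.1.1 the phase 2 primary outcome is DSMB advice that weighs QTc data, observed (S)AEs and stopping criteria. The pausing rules in protocol section 8 are single events or small counts. The secondary objective is to document adverse events. SAP 6.1 defines when non-inferiority is established for QTc only, so the sentence in SAP 2.3 can be called loose wording. All of this is right. A reader might infer that the plan would treat p > 0.05 as proof of safety; no passage says so, and the decision structure does not depend on it.

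Three further limits stand:

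- A reader might infer that liver safety as a whole has no between-arm comparison except a test of no difference on proportions. It does: ALT/AST values are also compared by ANCOVA or a t-test, and ANCOVA gives an estimated difference. The point is confined to adverse-event frequencies and the binary elevation. A difference in means does not bound the risk of rare large elevations.
- A reader might take 37% to 70% as a property of the design. It holds only for Fisher's test at assumed control rates of 10% and 5%; the table shows how far it moves.
- Counts by arm will be reported, so anyone could work out the risk difference and its limit. That makes the gap easy to close, but the plan still does not put the figure before the DSMB.

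On the conflict between the documents, the SAP cites protocol version 2.1, while the protocol text describes 2022 laboratory work as already done, so a version difference may explain it. The two still have to agree.

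**Conclusion.** The point holds in limited form. The non-inferiority wording is broader than the analysis behind it: mean QTc has a margin and ample power (99.6%), whereas adverse-event frequencies and ALT/AST elevations above 3x ULN have neither a margin nor a between-arm interval. The planned tests cannot support non-inferiority for those endpoints. How weak they are depends on event rates that the documents do not give: under Fisher, a doubling is missed about 91% of the time from 2%, 70% from 5%, 37% from 10% and 4% from 20%. These figures assume 150 analysable participants per arm and a two-sided 5% level.

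The consequence is incomplete information for the DSMB, not a flawed decision rule. The contradiction over comparing ALT/AST elevations is separate and does not depend on any assumed rate.

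**What to change.** 1. In SAP 6.2 and 6.3, keep the planned tests and add the risk difference (BE-PEP minus SDR-PEP) with its confidence limit, by Newcombe or Miettinen-Nurminen. Do this for each prespecified adverse-event group, any drug-related adverse event, and ALT/AST above 3x ULN. Fisher's test need not be removed, since protocol 9.2.2 prespecifies it for adverse events.
2. State in the SAP that a non-significant test is not evidence of equal safety.
3. In SAP 2.3 and protocol 4.3, limit the non-inferiority wording to mean QTc.
4. Make protocol 9.2.2 and SAP 6.2 agree on whether ALT/AST elevations are compared between arms.

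The cost is a few table columns, some SAP wording, and a small change to the protocol text. No new data are needed. Some safety statements will read less favourably, because the upper limits will be visible.
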